1.0 BACKGROUND

Cognitive biases (Cheng, et al., 2021) can lead to irrational decisions. Nudge theory exploits cognitive biases in rejecting the assumption that humans will make optimal choices when given access to the right information. Based on nudge theory, interventions have provided support for decision making on how to save for retirement and whether to donate an organ. **Nudge theory also offers novel solutions to improve decision making in health care** (Lamprell, Tran, Arnolda, & Braithwaite, 2021). Nudges present **subtle changes in the decision-making environment** that can influence behavior by exploiting cognitive biases without significantly restricting choice (Lamprell, Tran, Arnolda, & Braithwaite, 2021). Nudges can range from most restrictive (e.g., opt-out) to minimally restrictive (e.g., providing information). This project will test the use of nudges to influence providers' prescribing behavior.

Gaps in VA heart failure (HF) prescribing practices provide an opportunity to test the effectiveness of nudges to improve decision making for prescribing heart failure medications. Of VA patients with HF with reduced ejection fraction (HFrEF) only 22% of eligible patients are receiving SGLT2 inhibitors and only 39% are receiving MRAs (U.S. Department of Veterans Affairs, 2022); despite clinical effectiveness, clinical inertia and barriers have prevented greater adoption of these two foundational therapies. In this proposed study, we will evaluate two nudge interventions, **informational alerts (in CPRS) and peer comparison feedback emails**, to improve HF prescribing.

Prior experience: Our group has previously reported HF prescribing barriers for VA clinicians ([name], et al., 2016), and we believe that the strategies in this proposal will overcome these barriers. Provider-based barriers to MRA prescribing include unclear provider roles/responsibilities, difficulties coordinating care, and lack of knowledge/experience with the drug ([name], et al., 2016). Two small studies suggest that SGLT2 barriers are similar; cardiologists reported barriers to prescribing SGLT2s including potential adverse effects (hypoglycemia, urogenital infections), lack of knowledge/skills with drug, concerns about managing diabetes, and concerns of professional roles (perceived SGLT2 as outside their scope of responsibilities) (Cheng, et al., 2021) (Gao, Peterson, & Pagidipati, 2020).

Preliminary data: Informational alerts and peer comparison nudges have proven effective in other studies to change behavior. The PROMPT HF trial done in a university medical center demonstrated that informational alerts were associated with an increase in the number of GDMT medication classes prescribed (primary endpoint) from 19% to 26% ($p=.03$). One study compared individual audit feedback, peer comparison, and the combination, in a four-group design to influence clinician opioid prescribing in emergency care sites. They found a significant decrease in pills per prescription in the peer comparison arms.

We lack adequate knowledge about how to improve HF prescribing with nudges. Despite promising initial studies on the value of information alerts to improve HF prescribing, the improvements in prescribing were seen exclusively with beta-blockers, not in prescribing of SGLT2 inhibitors and MRAs – where the largest gaps exist in VA.

We need more information on whether combining nudges into multicomponent interventions is more effective.

A systematic review reported that only five of 48 nudge (10%) interventions in the literature were multicomponent; none of the studies were performed in the VA. For example, an evaluation active choice patient dashboard (delivered by email) with and without peer comparison to increase statin prescribing amongst PCPs found that only the active choice plus the peer comparison arm was associated with increased statin prescribing but not the active choice or the usual care arm alone. However, in these multicomponent trials, it is not clear which component is most impactful. Comparative effectiveness nudge trials are needed due to relative advantages and potential tradeoffs of each intervention. Further, research is needed to how nudges interact with one another and whether they may crowd each other out. In this proposal, we will evaluate whether informational alerts, peer comparison, or the combination of the two, is most effective.

This research will generate comparative evidence on which types and combinations of behavioral nudges work best. This study targets an HF treatment gap (SGLT2 and MRA) in which no prior nudge studies have demonstrated efficacy.

Our target population is clinicians in primary care and cardiology who are the main clinicians who treat HF. To incorporate the voice of the Veteran, we will meet with Veteran and Family Advisory Panel at SAVAHCS for feedback on the study design.

1.1 SIGNIFICANCE TO VETERANS AND/OR THE MISSION OF THE VA

Rates of HF GDMT have stagnated in the VA since 2013, and researchers have noted that 'new approaches to increase the uptake of evidence based HF treatment are urgently needed.' This proposal addresses several VA HSRD priority research areas including 'primary care practice and complex chronic disease management', 'quality and safety of care', and 'population health and whole health.' This application also addresses ORD-wide research priorities to 'increase substantial real-world impact of VA research' and 'putting VA data to work for Veterans.' **This proposed research will generate comparative evidence on which types and combinations of behavioral nudges work best.** Refinement of behavioral nudge interventions is likely to improve quality of VA HF management and effectiveness of HF care. This project leverages and enhances the existing VA PBM HF dashboard resource by testing new, user-centered implementation strategies. **By generating simple, scalable, and low-cost nudge strategies** directed at prescribing behavior, this proposal may extend the effectiveness of the VA PBM Academic Detailing program to improve medication prescribing across other therapeutic areas.

2.0 AIMS

Aim 1. Conduct a process evaluation ['PROCESS EVAL'] to develop two nudge strategies, an informational alert and peer comparison feedback, to encourage clinicians to prescribe MRA and SGLT2 inhibitors.

Aim 2. Evaluate preliminary outcomes ['NUDGE EFFECTIVENESS'] of the two nudge strategies to improve HF prescribing using the RE-AIM framework.

- a) Evaluate the preliminary Effectiveness of the alert and peer comparison strategies in a four-group design.
 - i) The four-groups to be compared are: control (no intervention), peer comparison email alone, information alert alone, and peer comparison/informational alert in combination. We will examine provider prescribing behavior and patient outcomes.
- b) Evaluate the implementation outcomes of the two nudge strategies.
 - i) We will report the following PRISM/RE-AIM outcomes: intervention, recipients, external environment, infrastructure, Reach, Adoption, and Implementation.

We hypothesize that an informational nudge and peer comparison will each increase prescribing compared to usual care (no nudge intervention). Further, we hypothesize that the combination of the two strategies will be more effective than either strategy alone.

3.0 SETTING & RESOURCES

Recruitment Clinic/areas	Primary care (all SAVAHCs sites at TUC and CBOCs) and Cardiology departments
Research location	SAVAHCS (Research Service [study coordinator], telework [PI, statistician, co-investigators, staff])
Study procedures location	SAVAHCS activities: 
 1. INTERVIEW/FOCUS GROUPS WITH CLINICIAN AND VETERAN ADVISORY PANEL: Virtually via TEAMS conferencing VA-Outlook, 2. NUDGE DELIVERY: Virtually via CPRS electronic record, VA Outlook, and VINCI/CDW (for patient outcomes data)

PERSONNEL RESOURCES	TOTAL
TUCSON	
Qualitative researcher (WOC)	2
Co-investigator, pharmacy (WOC)	1
Database manager, analyst (WOC)	1
Research coordinator/regulatory	1
PI	1
Co-investigator, nurse scientist	1
Consultant, behavioral economist	1
Statistician (WOC)	1

4.0 STUDY DESCRIPTION

4.1 STUDY DESIGN

TIMELINE				
	Startup Activities	Pre Nudge (control period)	Active Nudge Period	Post intervention period
Month (-12) to Month 0	Month 0-6	Month 7-9	Month 10-12	Month 13-18
	PROCESS EVALUATION			
	Interviews with clinicians; focus group with Veteran Council	Follow-up interviews and questionnaires with clinicians, follow-up focus group with Veteran Council		Focus groups with clinicians.
	NUDGE EFFECTIVENESS			
Patient data collection (to create peer comparison emails, need prior 12 month prescription information)				

AIM 1. – PROCESS EVALUATION. At the beginning of the study, we will conduct **interviews and focus groups** of SAVAHCs primary care and cardiology clinicians to understand clinician workflow, barriers, and feedback on proposed nudge interventions. We will also obtain **conduct focus groups with SAVAHCs Veteran Advisory Council**. After completing Aim 2, near the end of the study we will interview clinicians again and have them complete questionnaires regarding their opinions on the nudge interventions.

AIM 2. NUDGE EFFECTIVENESS. This is a pragmatic trial of cardiology and primary care clinicians at a single VA medical center. The trial will include a 3-month preintervention (observation) period and 3-month intervention period. In the intervention period, clinicians will be randomized to one of four nudge arms: usual care, informational alert, peer comparison feedback, and combination of alert and peer comparison.

Table 2. Study design			
	Peer comparison		
		Yes	No
Informational alert	Yes		
	No		

4.2 SUBJECT POPULATION

Study groups	Type of interaction	# screened for eligibility	# consent / chart review	# analysis	Comments
SAVAHCS prescribing clinicians (Primary Care, Cardiology)	Interview, focus group	Up to 100 (send invite to all Primary Care and Cardiology)	Up to 100 (consent for interview/focus group everyone accepting the invite)	Up to 100	ICF
	Nudge Interventions (alerts and emails)	N/A (all clinicians will be randomized)	Up to 100 (waiver of consent requested)	Up to 100	Waiver of consent
	Questionnaires	Up to 100	Up to 100 (waiver of documentation of consent requested)	Up to 100	Waiver of documentation consent
SAVAHCS Veteran and Family Advisory Panel	Focus group	Up to 20 (all panel members invited)	Up to 20	Up to 20	ICF – waiver of documentation (no recording)
SAVAHCS Patients with HF	Medical record review only	3000	1400	1400	HIPAA/PHI waiver

4.3 STUDY INTERVENTIONS

Aim 1. PROCESS EVALUATION

Interviews/questionnaires, and focus groups with clinicians:

Up to 100 cardiology and primary care prescribing clinicians [defined as: primary care NP/PA, physicians & cardiology NP/PA, physicians and cardiology specialty pharmacists] will be invited via email to participate in interviews. Qualitative interviewers will use a system thinking approach to map out steps and barriers and facilitators to the incorporation of the informational alert and peer comparison email into clinician workflow (Interview guide).

After the 3-months of informational alerts, all SAVAHCS clinicians who received a nudge will receive an email link to a 5-minute or less voluntary and confidential VA Redcap questionnaire with general questions about clinician demographics, work history, and the nudge's Acceptability, Feasibility, and Appropriateness.

Results from these interviews will be compiled to improve prescribing patterns and fit within the existing daily work that will be discussed in focus groups (up to 10 different cohorts [1 cohort can have 10 subjects, therefore 10 cohorts required] and up to 3 focus group sessions/cohort) of prescribing clinicians. Focus groups will include usability discussion of the alert and peer comparison prototypes (Figure 1). Aggregated de-identified information obtained in each focus group will be summarized and provided to all participants to check for accuracy.

Figure 1. Two Nudge Prototypes.

A. Informational alert	B. Peer comparison Email (Adapted ¹³)

Your patient has been identified in VA HF Dashboard as potentially eligible for an SGLT2 inhibitor. This alert is provided for informational purposes.
 
SGLT2 inhibitors are indicated in the 2022 ACC/AHA HF Guidelines (URL link provided) for patients with HFrEF (EF≤40%, NYHA class II-IV HF). Contraindications include urinary tract infection, eGFR < 25, type I diabetes.
 
Relevant data for this patient include: Prescription for beta blocker No prescription for ACE inhibitor LVEF 40% BNP 1550 Renal function: eGFR > 25
 
Suggested actions: Prescribe empagliflozin 10mg daily Alert primary care
 
If prescribing: Recommend checking renal function after starting therapy; reduce diuretic; watch for dehydration
	
Dear Dr. _____,
 
SAVAHCS Cardiology is working on new ways to help clinicians improve their patient's HF treatment. Based on AHA/ACC guidelines and the VA HF Dashboard, you have patients who could be on an SGLT2 inhibitor but have not been prescribed one.
 
Among eligible patients, your rolling 90-day SGLT2 prescribing rate: XX% [one of the following] Average of your peers at SAVAHCS: XX% Your top performing peers at SAVAHCS: XX%
 
If you have any questions, please email study coordinator XXX
 
Sincerely, XXXX Clinical Research Coordinator XXXX Study Principal Investigator

Focus group with SAVAHCS Veteran and Family Advisory Council

[figure not shown]
We will meet twice virtually with the Advisory Council during the study. We will ask for their feedback on their perceptions of study benefit and any suggestions for improvement. Unlike the other focus groups and interviews with clinicians, we will only take notes, but no audio

recording will occur. We will not ask for any individually identifiable information, only general feedback on the study.

Aim 2. NUDGE EFFECTIVENESS

Table 2. Study design			
	Peer comparison		
		Yes	No
Informational alert	Yes		
	No		

Informational Alert (in CPRS) and Peer Comparison Email for clinicians. (See Figure 1 above) During department meetings and by email, Primary Care and Cardiology clinicians will be notified about the goals of the study and will receive education on HF treatment guidelines to encourage optimal standard of care at baseline. Over the next 3 months, we will measure baseline rates of prescribing (SGLT2, MRAs); this will serve as control (pre-intervention period). Next, during the 3-month intervention period, clinicians will receive ‘nudges’ per their assignment to one of four groups. Those in the usual care arm will receive no other interventions. Clinicians in the alert only arm will receive an alert approximately two business days prior to a patient’s upcoming appointment. Clinicians will receive approximately one to two alerts per week or less. Clinicians assigned to peer comparison only, will receive messages by unencrypted email approximately every two weeks or even less often regarding their SGLT2i and MRA prescribing performance relative to their peers. We will review their prescribing activity for HF patients using VINCI/CDW data from the prior 12 months in order to generate these peer comparisons. Emails will be unencrypted because there is no PHI/PII. The clinicians in the combined alert and peer comparison arm will receive both interventions. All alerts and emails are based on HF patient data from VA PBM HF Dashboard, an operational/quality improvement dashboard available to all VA clinicians (https://vaww.pbi.cdw.va.gov/PBIRS/Pages/ReportViewer.aspx?/GPE/PBM_AD/SSRS/HeartFailure/HF_Dashboard) but most heavily utilized by pharmacists. (See sample screen from HF Dashboard below – no PHI)

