The study team will email/message the Advisory Panel coordinator to ask permission to be placed on the monthly Panel virtual meeting agenda. The study team will introduce the study objectives and explain that no individually identifiable data will be collected, only general study feedback.

Aim 2. NUDGE EFFECTIVENESS. A waiver of informed consent and PHI waiver are requested to review patient charts. The study staff will review the Pharmacy HF Dashboard to identify patient with upcoming primary care/cardiology appointments from which we will identify the patient and their corresponding clinician for whom to deliver the Alert or Email.

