5.3 INCLUSION/EXCLUSION CRITERIA

Activity	Aim 1.
Interview, focus groups of clinicians	All clinicians in Primary Care and Cardiology
Veterans and Family Advisory Council focus group	All participants at Council meeting
	Aim 2.
Patient record review to deliver nudges (CPRS alerts and peer comparison emails) to clinicians	
Patients meeting these criteria:
 
Inclusion Criteria:
 
 • HF patient • Scheduled cardiology or primary care appointment • Not being prescribed SGLT2 or MRA class medication 
Exclusion Criteria:
 
 • eGFR < 20 ml/min/1.73m² or potassium > 5.0

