5.4 SUBJECT PROCEDURES

5.4.1 SCREENING/ENROLLMENT/RANDOMIZATION

Activity	Screen	Enroll	Randomize
Interview, focus groups of clinicians	Invite all clinicians in Primary Care and Cardiology	Consent clinicians via Outlook/Teams	N/A
Questionnaires	Invite all clinicians who received nudges	Study Coordinator will send an email. (waiver of documentation of consent request)	N/A
Veterans and Family Advisory Council	Invite all Council members at scheduled Council meeting to participate	Interested Council members will verbally indicate consent to proceed with focus group	N/A
Deliver nudges (CPRS alerts and peer comparison emails) to clinicians	Study coordinator will identify eligible HF patient encounters (see inclusion/exclusion above)	Study coordinator will deliver nudge based on assigned nudge group (waiver of consent request)	VA Redcap will be utilized to randomly assign each clinician to nudge type (alert, email)

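### The Aim 2 patient screen excludes only eGFR below 20, while the prototype SGLT2 alert lists eGFR below 25 as a contraindication; unless the HF Dashboard already filters them, patients with eGFR 20 to below 25 could trigger an alert that contradicts its own suggestion

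*Combined protocol and SAP*

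**What the plan says.** Section 5.3 gives a single set of patient criteria for delivering both alerts and emails, covering both drug classes. On renal function it excludes "eGFR < 20 ml/min" (per 1.73m²); the only other exclusion is potassium above 5.0. There is no separate renal limit for SGLT2 inhibitors.

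Section 5.4.1 makes these criteria operative: "Study coordinator will identify eligible HF patient encounters (see inclusion/exclusion above"). The coordinator then delivers the nudge to which the clinician was assigned.

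The prototype alert in section 4.3, Figure 1A, is specific to SGLT2 inhibitors. It says "Contraindications include urinary tract infection, eGFR < 25, type I diabetes", shows the sample data line "Renal function: eGFR > 25", and lists "Prescribe empagliflozin 10mg daily" among its suggested actions.

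The HF Dashboard also plays a part in selection. The alert describes the patient as "identified in VA HF Dashboard as potentially eligible for an SGLT2 inhibitor". The Aim 2 text of section 4.3 adds: "All alerts and emails are based on HF patient data from VA PBM HF Dashboard". Section 5.1 says: "The study staff will review the Pharmacy HF Dashboard to identify patient with upcoming primary care/cardiology appointments". The dashboard's eligibility rules, including any eGFR limit, are not in the documents.

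**The concern.** The screen that decides whether an alert is sent and the alert itself use different numbers for the same laboratory value. Nothing in the plan says which number governs SGLT2 alerts, and nothing describes a step that withholds an SGLT2 alert between the two.

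At stake is the content of the intervention at a threshold that bears on patient safety. A clinician could receive a prompt to prescribe a drug for a patient whose eGFR the same prompt names as a reason not to. That also sits poorly with two arguments made elsewhere in the protocol. Section 5.2 supports the consent waiver partly by saying that every recommendation follows national and VA guidelines. Section 7.0 relies on guideline-recommended use in explaining why no DSMB is needed.

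**Working it through.** The plan states no figure that needs reproducing, and the point does not depend on sample size, power or alpha. The check compares the two stated rules.

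**Inputs**

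| Element | Rule | Where |
|---|---|---|
| Patient screen | Excluded if eGFR < 20, so eGFR ≥ 20 passes | Section 5.3, Aim 2 |
| Use of the screen | Coordinator selects encounters by it, then delivers the nudge | Section 5.4.1 |
| Alert contraindication | eGFR < 25 | Section 4.3, Figure 1A |
| Alert sample data line | eGFR > 25 | Section 4.3, Figure 1A |
| Alert suggestion | Prescribe an SGLT2 inhibitor | Section 4.3, Figure 1A |
| Dashboard SGLT2 limit | Not given; call it *d* | Not in the documents |

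**Step 1: the written rules alone.** Passing the screen means eGFR ≥ 20. Being contraindicated by the alert means eGFR < 25. Both hold when 20 ≤ eGFR < 25, a band of 25 − 20 = 5 ml/min/1.73m². The endpoints matter: a value of exactly 20 is not excluded by the screen, and a value of exactly 25 is not contraindicated by the alert.

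**Step 2: allowing for the dashboard.** If the dashboard flags SGLT2 candidates only at eGFR ≥ *d*, a patient must have eGFR of at least max(20, *d*) to reach the alert. The conflicting band is then max(20, *d*) ≤ eGFR < 25.

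- If *d* is 25 or more, the band is empty and no contradictory alert is sent.
- If *d* is 20 or less, or there is no renal filter, the band is the full 20 to below 25.
- If *d* lies between 20 and 25, part of the band remains.

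The documents do not say which case applies.

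**Step 3: is 25 a slip?** The alert uses 25 twice, once as the contraindication and once in the data line, so a single mistyped digit is unlikely. The data line is ambiguous beyond that. It is written as a threshold check and not as a patient's value, so it may hint that SGLT2 alerts were meant to be built around 25. Section 5.3 does not say so.

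**Step 4: after alignment.** With 25 as the SGLT2 limit in both places, passing means eGFR ≥ 25 and contraindicated means eGFR < 25, so the overlap is empty. With 20 in both places, passing means eGFR ≥ 20 and contraindicated means eGFR < 20, so the overlap is again empty. Either choice removes the conflict whatever *d* is.

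**The case against.** The strongest reply has three parts.

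First, Figure 1 is labelled a prototype. Aim 1 exists to develop the nudges, the prototypes go to focus groups, and section 5.2 speaks of co-designing them. The final wording is not in the documents, so the protocol does not commit to sending the figure of 25. This stands as a limit on severity. It does not dispose of the point: this is the only alert wording in the protocol, the Aim 2 description refers back to it, and the focus-group discussion is described as being about usability, with no stated step for reconciling thresholds.

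Second, section 5.3 can be read as an outer limit shared by two drug classes, with drug-specific eligibility set by the dashboard. On that reading the band may never reach an SGLT2 alert. This also stands, and it is why the point is conditional. A reader might infer that patients with a listed contraindication will be the subject of alerts; the documents do not support that without the dashboard's rules.

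Third, the alert is informational, it displays renal data beside the contraindication, and section 5.2 says clinicians need not follow it. These safeguards lower the risk but leave the mismatch in place.

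A reader might also extend the point to ejection fraction and type I diabetes, which the alert mentions and section 5.3 does not. That is missing detail, not a conflict between two stated rules, and the dashboard flag may cover both. It forms no part of this point.

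**Conclusion.** The inconsistency is real and minor. Two stated SGLT2-relevant cut-offs differ by 5 ml/min/1.73m², and no section reconciles them. That the texts disagree is certain. That a self-contradicting alert would actually be sent is conditional on two things: that the dashboard's SGLT2 flag does not already remove the band, and that the prototype's wording carries through to the delivered alert.

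No patient count is offered. It is tempting to scale from the planned numbers, but the documents give no eGFR distribution. The 168 per group in section 8.0 is a power requirement, while section 4.2 plans 1400 patients for analysis, so neither gives a sound base or ceiling. The number affected may be zero.

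A reader might also infer a bias in the comparison of arms. The documents do not support that: neither the size nor the direction of any effect can be derived from them, and none is claimed. Nor can they settle which of 20 and 25 is clinically right.

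**What to change.** Before the active nudge period (months 10 to 12 in the section 4.1 timeline), use one SGLT2 eGFR cut-off in the screen and in the alert. The clinical leads should choose between:

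- **25 in both places.** Add to section 5.3 an exclusion of eGFR below 25 that applies to SGLT2 alerts only, keeping the limit of below 20 otherwise.
- **20 in both places.** Leave section 5.3 as it is, and change both the contraindication and the renal data line in the Figure 1A alert to 20.

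The cost is a short wording amendment while the prototype is being finalised. Choosing 25 may slightly reduce the number of SGLT2-eligible encounters. If the dashboard flag turns out to apply that limit already, the amendment only records existing practice and no encounters are lost.
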